4.1 Rationale for study design

This randomized, double-blind, parallel-group, placebo-controlled, design supports the rigorous assessment of efficacy as well as safety of ruxolitinib as add-on to SoC therapy for patients with COVID-19 pneumonia.

Screening Period

The screening period allows for assessment of patient entry criteria to ensure suitable patients are entered into the study. Screening and randomization may occur on the same day.

Study Period

During this period, oral ruxolitinib 5 mg twice daily or oral matching-image placebo twice daily (randomized 2:1) will be administered 14 days. An additional 14 days of study drug may be given, if in the opinion of the investigator, the patient's clinical signs and symptoms are not improved or worsen and the potential benefit outweighs the potential risk. The endpoints included in this study measure clinical status, clinical and in-hospital outcomes, and laboratory values during the 29-day Study Period. These measurements are consistent with endpoints and measurement times for other studies of therapies in the treatment of COVID-19 ([WHO 18-Feb-2020](#); [Cao et al 2020](#)).

4.2 Rationale for choice of background therapy

Although there are no approved treatments for COVID-19, SoC therapy for patients with COVID-19 pneumonia generally includes supportive care and anti-viral treatments. Thus, placebo + SoC therapy is appropriate as a control in this study.

4.3 Rationale for dose/regimen and duration of treatment

The ruxolitinib dose regimen chosen in this study is the lowest efficacious dose based on pharmacokinetic data. Ruxolitinib 5 mg twice daily is the approved starting dose for treatment of steroid-refractory acute graft versus host disease in the US with demonstrated anti-inflammatory effect ([Jagasia et al 2020](#)). Ruxolitinib 5 mg twice daily is also the starting dose recommended for patients with myelofibrosis when platelets are $50 \times 10^9/L - <100 \times 10^9/L$.

[Cao et al \(2020\)](#) reported the median hospital stay for COVID-19 was 12 days with an interquartile range of 1 to 14 days. Therefore, a duration of treatment for 14 days seems reasonable and has been selected for this study. An additional 14 days of study drug may be given, if in the opinion of the investigator, the patient's clinical signs and symptoms are not improved or worsen and the potential benefit outweighs the potential risk.

4.4 Rationale for choice of control drugs (comparator/placebo) or combination drugs

The study will evaluate the efficacy and safety of oral ruxolitinib + SoC therapy, compared with matching-image placebo + SoC therapy. Despite the lack of targeted treatments for COVID-19, SoC for patients with severe COVID-19 respiratory disease generally includes supportive care and may include available anti-viral agents. Therefore, SoC + placebo treatment is appropriate as a control in this study.

4.5 Purpose and timing of interim analyses/design adaptations

No interim analysis is planned. An internal Data Monitoring Committee at Novartis will be established to conduct periodic unblinded safety reviews.

4.6 Risks and benefits

There is preclinical evidence from both laboratory and animal models that blockade/inhibition of the JAK/STAT pathway could have a beneficial effect on the CRS and the course of severe respiratory disease/ARDS in patients with COVID-19. Additionally, there is some clinical evidence of efficacy with ruxolitinib in pilot studies in another recognized disease with CRS: secondary HLH (See [Section 1.1.1](#)). However, ruxolitinib has not previously been studied in patients with COVID-19 pneumonia. Therefore, it is unknown as to whether there will be a benefit for patients being treated with ruxolitinib in this disease.

The primary clinical risks with ruxolitinib treatment are the potential sequelae of decreased hematopoietic proliferation attributable to the inhibition of growth factor pathways associated with JAK inhibition. In the Phase 3 clinical studies of ruxolitinib in patients with myelofibrosis, which involved longer-term dosing and, in general, higher doses than that proposed in this protocol, the most frequent treatment-emergent adverse events (AEs) were dose-dependent, reversible thrombocytopenia, anemia, and neutropenia. The above events could increase the risk of infection, including pneumonia and bronchitis, possibility of developing anemia, bleeding, fatigue, and/or shortness of breath. In healthy volunteers, rheumatoid arthritis patients, and patients with pancreatic cancer or hormone-refractory prostate cancer, the effects on hematopoietic proliferation are less pronounced, presumably because of greater bone marrow reserve. The most frequent non-hematologic AEs were mild, reversible increases in alanine aminotransferase (ALT) and aspartate aminotransferase (AST); bruising; hypercholesterolemia; dizziness; headache; and urinary tract infections. Tuberculosis has been infrequently reported in patients receiving ruxolitinib to treat myelofibrosis (<1/100 patients). The symptoms of tuberculosis include chronic cough with blood-tinged sputum, fever, night sweats, and weight loss. There may be risks associated with rapid discontinuation of ruxolitinib.

Patients with myelofibrosis, particularly those who have stopped taking ruxolitinib suddenly, have reported return of MF symptoms such as fatigue, bone pain, fever, pruritus, night sweats, symptomatic splenomegaly and weight loss. In very few patients, respiratory distress, disseminated intravascular coagulation (DIC), multiorgan failure have been reported.

Hepatitis B viral load increases, with and without associated elevations in ALT and AST, have been reported in patients with chronic hepatitis B infections taking ruxolitinib. The effect of ruxolitinib on viral replication in patients with chronic hepatitis B virus is unknown. A rare

disease called progressive multifocal leuko-encephalopathy (PML), has been reported with ruxolitinib. It is important to note that PML and infections are complications associated with MF that has been previously described in the absence of ruxolitinib. Additionally, non-melanoma skin cancers (NMSCs), including basal cell, squamous cell, and a rare and aggressive type of skin cancer called merkel cell carcinoma has been reported in patients who took ruxolitinib, it is unknown whether this was due to ruxolitinib treatment.

In the presence of potent CYP3A4 inhibitors, there is the possibility of increased exposure to ruxolitinib and more frequent monitoring of hematology parameters is recommended, although no automatic dose adjustment of ruxolitinib is required. See [Appendix 4](#) for a list of cytochrome P450 3A4 (CYP3A4) inhibitors and inducers.

For a comprehensive assessment of the risks of ruxolitinib, refer to the Investigator Brochure.

5 Study Population

5.1 Inclusion criteria

Participants eligible for inclusion in this study must meet **all** of the following criteria:

1. Patient or guardian/health proxy must provide informed consent (and assent if applicable) before any study assessment is performed.
2. Male and female patients aged ≥ 12 years (or \geq the lower age limit allowed by Health Authority and/or Ethics Committee/Institutional Review Board approvals).
3. Patients with coronavirus (SARS-CoV-2) infection confirmed by polymerase chain reaction (PCR) test or another rapid test from the respiratory tract prior to randomization.
4. Patient is currently hospitalized or will be hospitalized prior to randomization.
5. Patients, who meet **at least one** of the below criteria:
 - Pulmonary infiltrates (chest X ray or chest CT scan);
 - Respiratory frequency ≥ 30 /min;
 - Requiring supplemental oxygen;
 - Oxygen saturation $\leq 94\%$ on room air;
 - Arterial oxygen partial pressure (PaO₂)/ fraction of inspired oxygen (FiO₂) < 300 mmHg (1mmHg=0.133kPa) (corrective formulation should be used for higher altitude regions (over 1000m)).

5.2 Exclusion criteria

Participants meeting **any** of the following criteria are **not** eligible for inclusion in this study.

1. History of hypersensitivity to any drugs or metabolites of similar chemical classes as ruxolitinib.
2. Presence of severely impaired renal function defined by serum creatinine > 2 mg/dL (>176.8 $\mu\text{mol/L}$), or have estimated creatinine clearance < 30 ml/min measured or calculated by Cockcroft Gault equation or calculated by the updated bedside Schwartz equation.
3. Suspected uncontrolled, active bacterial, fungal, viral, or other infection (besides COVID-19).
4. Current or history of active TB infection.
5. History of progressive multifocal leukoencephalopathy (PML).
6. Currently intubated or intubated between screening and randomization.
7. In intensive care unit (ICU) at time of randomization.
8. Patients who are on anti-rejection, immunosuppressant or immunomodulatory drugs (i.e. tocilizumab, ruxolitinib, canakinumab, sarilumab, anakinra).
9. Intubated or in ICU for COVID-19 disease prior to screening.
10. Participating in any other investigational or interventional trials.
11. Unable to ingest tablets at randomization.
12. ALT ≥ 5 x ULN detected at screening (according to local laboratory reference ranges).
13. Patients who have evidence of liver cirrhosis (Child A to C).
14. ANC $< 1000/\mu\text{L}$ at screening.
15. Platelet count $< 50,000/\mu\text{L}$ at screening.
16. Pregnant or nursing (lactating) women.
17. Females ≥ 12 and < 18 years of age and of childbearing potential (e.g. are menstruating) who do not agree to abstinence or, if sexually active, do not agree to the use of highly effective contraception as defined below, throughout the study and for up to 30 days after stopping treatment,

OR

Females ≥ 18 years of age and of child-bearing potential, defined as all women physiologically capable of becoming pregnant, unless they are using highly effective methods of contraception as defined below, throughout the study and for up to 30 days after stopping treatment.

Highly effective contraception methods include:

- Total abstinence (when this is in line with the preferred and usual lifestyle of the patient). Periodic abstinence (e.g., calendar, ovulation, symptothermal, post-ovulation methods) and withdrawal are not acceptable methods of contraception.
- Female sterilization (have had surgical bilateral oophorectomy with or without hysterectomy), total hysterectomy or tubal ligation at least six weeks before taking study treatment. In case of oophorectomy alone, only when the reproductive status of the woman has been confirmed by follow up hormone level assessment.

- Male sterilization (at least 6 months prior to screening). The vasectomized male partner should be the sole partner for that patient.
- Use of oral, injected or implanted hormonal methods of contraception. Placement of an intrauterine device (IUD) or intrauterine system (IUS) or other forms of hormonal contraception that have comparable efficacy (failure rate <1%), for example hormone vaginal ring or transdermal hormone contraception (in case of oral contraception, patients should have been using the same pill on a stable dose for a minimum of 3 months before Screening).

Women are considered post-menopausal and not of child bearing potential if they have had 12 months of natural (spontaneous) amenorrhea with an appropriate clinical profile (e.g. age appropriate, history of vasomotor symptoms) or have had surgical bilateral oophorectomy (with or without hysterectomy), total hysterectomy or tubal ligation at least six weeks ago. In the case of oophorectomy alone, only when the reproductive status of the woman has been confirmed by follow up hormone level assessment is she considered not of child bearing potential.

6 Treatment

6.1 Study treatment

6.1.1 Investigational and control drugs

Ruxolitinib 5 mg tablets or matching placebo will be administered orally twice per day approximately 12 hours apart (morning and night) without regards to food.

Dose reductions or interruptions for any toxicity attributed to study drug are permitted in order to allow the patient to continue on the study treatment. See [Section 6.6.2](#).

If a patient becomes intubated during the course of the study, study drug can be administered as follows ([Jakafi 2011](#)):

- For patients unable to ingest tablets, study drug can be administered through a nasogastric tube (8 French or greater) as follows:
 - Suspend one tablet in approximately 40 mL of water with stirring for approximately 10 minutes.
 - Within 6 hours after the tablet has dispersed, the suspension can be administered through a nasogastric tube using an appropriate syringe.
- The tube should be rinsed with approximately 75 mL of water

Table 6-1 Investigational and control drug

Investigational/ Control Drug	Pharmaceutical Dosage Form	Route of Administration	Supply Type
INC424 5mg	Tablet	Oral use	Double-blind supply; bottles
INC424 Placebo to 5mg	Tablet	Oral use	Double-blind supply; bottles

6.1.2 Supply of study treatment

No additional treatment beyond ruxolitinib 5 mg or matching image placebo will be provided.

6.1.3 Treatment arms/group

Participants will be assigned at randomization to one of the following treatment arms/groups in a ratio of 2:1:

- ruxolitinib 5 mg tablets twice daily; or
- matching image placebo tablets twice daily.

6.1.4 Treatment duration

The planned duration of treatment is 14 days. An additional 14 days of study drug may be given, if in the opinion of the investigator, the patient's clinical signs and symptoms are not improved or worsen and the potential benefit outweighs the potential risk. Participants may be discontinued from treatment earlier due to unacceptable toxicity, disease progression and/or treatment is discontinued at the discretion of the investigator or the participant. Treatment will not be provided upon completion of the study.

6.2 Other treatments

6.2.1 Concomitant therapy

All medications, procedures, and significant non-drug therapies (including physical therapy and blood transfusions) administered after the participant was enrolled into the study must be recorded on the appropriate electronic Case Report Forms (eCRFs).

Each concomitant drug must be individually assessed against all exclusion criteria/prohibited medication. If in doubt, the investigator should contact the Novartis medical monitor before randomizing a participant or allowing a new medication to be started. If the participant is already enrolled, contact Novartis to determine if the participant should continue participation in the study.

The patient must be told to notify the Treating Physician about any new medications he/she takes after the start of study drug.

6.2.1.1 Permitted concomitant therapy requiring caution and/or action

Patients may receive: anti-virals, inhaled or systemic corticosteroids, heparin, low molecular weight heparin (LMWH), direct oral anticoagulants, anti-emetics, calcineurin inhibitors, azole fungal prophylaxis, broad spectrum antibiotics (either semi-synthetic penicillin or third generation cephalosporin with vancomycin, gentamycin or equivalent), acyclovir prophylaxis, G-CSF, steroid pre-meds prior to RBC/platelet transfusions, narcotics, and sedatives warrant close monitoring of potential drug-drug interaction effects of these concurrent drugs.

Use of oral, injected or implanted hormonal methods of contraception are allowed while on study drug.

In patients taking warfarin, heparin, LMWH, or direct oral anticoagulants, the degree of thrombocytopenia should be considered, platelet counts and coagulation parameters monitored, and the dose of anti-coagulant or non-steroidal anti-inflammatory drug adjusted accordingly.

In patients taking drugs that affect platelet function/count, the degree of thrombocytopenia should be considered, platelet counts and coagulation parameters monitored, and the dose of drug adjusted accordingly.

In the presence of potent CYP3A4 inhibitors, there is the possibility of increased exposure to ruxolitinib and more frequent monitoring of hematology parameters is recommended, although no automatic dose adjustment is required. See [Appendix 4](#) for a list of cytochrome P450 3A4 (CYP3A4) inhibitors and inducers.

The patient and the treating physician should be aware of potential signs of overdose of the concomitant medications and in the event of suspected study drug related toxicity; administration of study drug should be dose reduced or held according to the treating physician's judgement.

For additional information, please refer to the Investigator Brochure.

6.2.2 Prohibited medication

The following medications are prohibited until treatment discontinuation:

- Concomitant use of another JAK inhibitor
- Aspirin in doses >150 mg/day
- Fluconazole > 200 mg daily

For additional information, please refer to the Investigator Brochure.

6.3 Participant numbering, treatment assignment, randomization

6.3.1 Participant numbering

Each participant is identified in the study by a Participant Number (Participant No.), that is assigned when the participant is enrolled for screening and is retained for the participant throughout his/her participation in the trial. The Participant No. consists of the Center Number (Center No.) (as assigned by Novartis to the investigative site) with a sequential participant number suffixed to it, so that each participant's participation is numbered uniquely across the

entire database. Upon completion of informed consent, the participant is assigned to the next sequential Participant No. available.

Screen failures cannot be rescreened. Screen failures should be called into IRT.

6.3.2 Treatment assignment, randomization

At the randomization visit, all eligible participants will be randomized via Interactive Response Technology (IRT) to one of the treatment arms. The investigator or his/her delegate will contact the IRT after confirming that the participant fulfills all the inclusion/exclusion criteria. The IRT will assign a randomization number to the participant, which will be used to link the participant to a treatment arm and will specify a unique medication number for the first package of study treatment to be dispensed to the participant.

The randomization numbers will be generated using the following procedure to ensure that treatment assignment is unbiased and concealed from participants and investigator staff. A participant randomization list will be produced by the IRT provider using a validated system that automates the random assignment of participant numbers to randomization numbers. These randomization numbers are linked to the different treatment arms, which in turn are linked to medication numbers. A separate medication list will be produced by or under the responsibility of Novartis Global Clinical Supply (GCS) using a validated system that automates the random assignment of medication numbers to packs containing the study treatment.

Randomization will be stratified by regions. Stratification ensures a balanced allocation of subjects to treatment groups within the strata.

The randomization scheme for subjects will be reviewed and approved by a member of the Randomization Office.

6.4 Treatment blinding

Participants, investigator staff, persons performing the assessments, and CTT will remain blind to the identity of the treatment from the time of randomization until database lock, using the following methods: (1) Randomization data are kept strictly confidential until the time of unblinding and will not be accessible by anyone else involved in the study, (2) the identity of the treatments will be concealed by the use of study treatment that are all identical in packaging, schedule of administration, appearance, taste, and odor.

Unblinding will occur in the case of participant emergencies and at the conclusion of the study.

6.5 Dose escalation and dose modification

Study drug dose adjustments and/or interruptions are described in [Section 6.6.2](#).

6.5.1 Dose modifications

Dose reductions or interruptions for patients that do not tolerate the dosing schedule and are attributed to study drug are permitted in order to allow the patient to continue on the study treatment (see [Section 6.6.2](#) for more guidance).

Dose modifications must be reported in the appropriate eCRFs.

For subjects with moderate renal impairment (creatinine clearance (CrCl) 30–59 mL/min) or any level of hepatic impairment, i.e. Mild, Moderate, or Severe (Child-Pugh categories A, B, C), AND platelet counts between 50 – 100 X 10⁹ /L, the dose should be reduced to one tablet per day.

If renal/hepatic impairment AND platelet count improves > 100x 10⁹/L, dosing may be resumed at one tablet twice per day.

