6.6.2 Recommended treatment of adverse events

Dose reductions or interruptions for patients that do not tolerate the dosing schedule and are attributed to study drug are permitted in order to allow the patient to continue on the study treatment. Adverse events will be assessed and graded according to the Common Terminology Criteria for Adverse Events (CTCAE) Version 5.0 as described in [Section 10.1.1](#).

Neutropenia (Growth factor supplementation and transfusion should be provided as clinically indicated.)

Grade 3 (ANC < 750 - 500/mm³): Reduce dose to one tablet per day, monitor ANC daily until resolved to ≤ Grade 2, then resume initial dose level.

Grade 4 (ANC < 500/mm³): Hold dose, monitor ANC daily until resolved to ≤ Grade 3, then resume with reduced dose of one tablet per day. If resolves to ≤ Grade 2, can resume initial dose level.

Thrombocytopenia (transfusion support should be provided as clinically indicated)

For platelet counts < 20,000/mm³: Hold dose until resolved to > 35,000/mm³, then resume at a reduced dose level of one tablet per day. If counts are stable, dose may be cautiously re-escalated.

Dose reductions or interruptions for non-hematologic toxicity are permitted in order to allow the patient to continue on the study treatment. Dose adjustments for different ranges of non-hematologic toxicity are described below. The objective of the dose adjustment rules is to optimize treatment response for each individual patient while avoiding significant non-hematologic toxicities.

AST/ALT elevation

See [Appendix 1](#) for stopping or interrupting study drug for elevated ALT/AST.

Other adverse events (non-hematological) attributed to study drug

Recommendation for Grade 1 or 2: Maintain dose level.

Grade 3: Hold dose until resolved to baseline or Grade 1.

Grade 4: Discontinue from study treatment.

Medication used to treat adverse events (AEs) must be recorded on the appropriate eCRF.

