9.1 Discontinuation and completion

9.1.1 Study treatment discontinuation and study discontinuation

Discontinuation of study treatment for a participant occurs when study treatment is stopped earlier than the protocol planned duration and can be initiated by either the participant or the investigator.

The investigator must discontinue study treatment for a given participant if, he/she believes that continuation would negatively impact the participant's well-being.

Study treatment must be discontinued under the following circumstances:

- Participant/guardian decision
- Pregnancy
- Use of prohibited treatment as per recommendations in the prohibited treatment section
- Abnormal liver laboratory results as specified in [Appendix 1](#)
- Grade 4 non-hematologic adverse events attributed to study drug
- Any situation in which study participation might result in a safety risk to the participant
- Following emergency unblinding
- Any laboratory abnormalities that in the judgment of the investigator, taking into consideration the participant's overall status, prevents the participant from continuing participation in the study

If discontinuation of study treatment occurs, the investigator should make a reasonable effort to understand the primary reason for the participant's premature discontinuation of study treatment and record this information.

Participants who discontinue study treatment or who decide they do not wish to participate in the study further should NOT be considered withdrawn from the study UNLESS they withdraw their consent (see 'Withdrawal of Informed Consent' section). **Where possible, they should return for the assessments indicated** in the Assessment Schedule. If they fail to return for these assessments for unknown reasons, every effort (e.g. telephone, e-mail, letter) should be made to contact the participant/pre-designated contact as specified in the lost to follow-up section. This contact should preferably be done according to the study visit schedule.

If the participant cannot or is unwilling to attend any visit(s), the site staff should maintain regular telephone contact with the participant, or with a person pre-designated by the participant. This telephone contact should preferably be done according to the study visit schedule.

After study treatment discontinuation, at a minimum, in abbreviated visits, the following data should be collected at clinic visits or via telephone/email contact:

- New / concomitant treatments

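### Section 6.5.1's reduction trigger stops at platelets 50 × 10⁹/L and CrCl 30 mL/min, so some worse on-study states have no threshold-based reduction although a milder state requires one

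*Protocol*

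**What the plan says.** The reduction rule in Protocol Section 6.5.1 has two limbs that must both be met. The organ-function limb is "For subjects with moderate renal impairment (creatinine clearance (CrCl) 30–59 mL/min) or any level of hepatic impairment", which the text extends to all three Child-Pugh categories. The platelet limb and the action are "AND platelet counts between 50 – 100 X 10⁹ /L, the dose should be reduced to one tablet per day". The way back is "If renal/hepatic impairment AND platelet count improves > 100x 10⁹/L, dosing may be resumed at one tablet twice per day".

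Section 6.6.2 holds the drug when platelets fall below 20,000/mm³ and allows a restart above 35,000/mm³, where the instruction is: "then resume at a reduced dose level of one tablet per day. If counts are stable, dose may be cautiously re-escalated". It sets no platelet action between 20 and 50 × 10⁹/L.

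Entry is limited by Section 5.2. Patients who "have estimated creatinine clearance < 30 ml/min" are excluded, as are those with platelets below 50,000/µL at screening. Exclusion 13 also bars "Patients who have evidence of liver cirrhosis (Child A to C").

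Section 9.1.1 lists circumstances in which treatment must stop. They include "Any situation in which study participation might result in a safety risk to the participant" and "Any laboratory abnormalities that in the judgment of the investigator" rules out continuing.

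**The concern.** A dose rule should not become less cautious as the patient gets worse. Here a patient with CrCl 45 mL/min and platelets of 70 × 10⁹/L must go to one tablet a day. A patient with the same CrCl and platelets of 40, or with platelets of 70 and CrCl of 25, meets no numeric reduction.

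The protocol foresees patients of this kind. Section 1.1 names acute kidney injury and multiorgan failure as complications of the disease. The outcome scale in Section 8.3.1 includes renal replacement therapy, and Section 6.1.1 lets dosing continue by nasogastric tube after intubation. Section 4.6 lists dose-dependent thrombocytopenia among the main risks of the drug. What is at stake is patient safety in this group, and consistency between sites facing the same laboratory values.

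**Working it through.** No sample size or error rate enters this check. It is a check of rule coverage.

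**Inputs.**
- Reduction rule: Section 6.5.1.
- Hold rule: Section 6.6.2.
- Entry limits: Section 5.2.
- Units: 1,000/mm³ (or per µL) = 1 × 10⁹/L. The hold is therefore at 20, the restart at 35 and the platelet entry limit at 50 × 10⁹/L.

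**Step 1: written threshold action, no hepatic impairment.**

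| Platelets (× 10⁹/L) | CrCl ≥60 | CrCl 30–59 | CrCl <30 |
|---|---|---|---|
| >100 | none | none | none |
| 50–100 | none | **reduce** | none |
| 20–49 | none | none | none |
| <20 | hold | hold | hold |

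Five other cells are at least as bad as the trigger cell on both axes. Two of them, with platelets below 20, are covered by the hold. That leaves 5 − 2 = 3 cells with a weaker written action than the milder trigger cell: 20–49 with CrCl 30–59, 50–100 with CrCl <30, and 20–49 with CrCl <30.

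**Step 2: the same grid with hepatic impairment.** The hepatic limb has no upper severity limit, so the 50–100 row reads reduce at every renal level, including CrCl <30. The 20–49 row still reads none throughout. Only that platelet band is open. It should be rare, because cirrhosis is excluded at entry and acute liver events have their own rules in Appendix 1.

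**Step 3: can a patient be in an open cell on twice-daily dosing?** A patient who passes through the trigger cell is already on one tablet, and the written return needs improvement, so further worsening does not restore the dose. The gap affects patients who bypass that cell:
- Entry at platelets 50–100 and CrCl ≥60 (twice daily, no rule applies). Platelets fall to 20–49, then CrCl falls to 30–59.
- Entry at platelets >100 and CrCl 30–59 (twice daily, no rule applies). CrCl falls below 30, then platelets fall to 50–100.

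Neither needs an abrupt drop. Given the entry limits, both arise only after screening.

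**Step 4: dose at stake.** Two tablets × 5 mg = 10 mg/day, against one tablet × 5 mg = 5 mg/day. Treatment lasts 14 days, with a possible 14 more. The excess would last only from the deterioration onward.

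**Step 5: comparison within Section 6.6.2.** Neutropenia is stepped: reduce at Grade 3, hold at Grade 4. Platelets have no such step. A patient recovering from a hold to a count of 40 restarts on one tablet. A patient falling to 40 for the first time has no written reduction, even with moderate renal impairment.

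**Step 6: proposed rule.** With CrCl <60 and platelets ≤100, the three open cells in Step 1 become reduce, as does the whole 20–49 row in Step 2. No inverted cell remains in either grid.

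**The case against.** **The floors match the entry limits.** CrCl below 30 and platelets below 50 are both excluded, so the renal range covers every eligible patient at baseline, and Section 6.5 sends dose adjustments to Section 6.6.2. This probably explains how the floors arose. It does not settle the matter: the return condition in Section 6.5.1 is about changes over time, so the rule also operates on study, where the entry limits no longer hold.

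**Other provisions apply.** A reader might infer that these patients are unprotected, or that stopping under Section 9.1.1 is their only cover. The documents do not support either reading:
- Section 6.2.1.1 directs a reduction or hold, at the physician's judgement, for suspected drug toxicity.
- Sections 6.5.1 and 6.6.2 permit reductions and interruptions attributed to study drug.
- Section 6.6.2 holds for attributed Grade 3 and discontinues for attributed Grade 4 non-haematological events.
- Section 9.1.1 requires stopping for a possible safety risk, with no attribution needed. That is a stronger action than one tablet a day.

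This objection stands as far as protection goes. It does not supply the missing threshold. Section 10.1.1 tells investigators that events due to progression of the illness will usually be classed as not suspected, so disease-driven platelet or renal decline may not activate the attribution-based clauses. Section 9.1.1 gives no number and only the option to stop.

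**The threshold is a clinical choice.** Having no platelet step between 20 and 50 for patients without organ impairment is the sponsor's decision and is not contested. The point concerns only patients worse off than a state for which the protocol itself requires a reduction.

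**Re-escalation.** A reader might also see a conflict between the Section 6.5.1 return condition and re-escalation on stable counts in Section 6.6.2. The latter is permissive and needs an earlier count below 20. It is not a contradiction.

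**Conclusion.** The trigger in Section 6.5.1 is inverted as written. Without hepatic impairment, three worse states carry no threshold-based reduction; with hepatic impairment, one platelet band does. What is missing is a numeric trigger, since attribution- or judgement-based reduction, hold and stopping remain available throughout.

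This rests on a literal reading of the two bounded ranges and on counting only actions tied to a stated platelet or CrCl value. The grid counts describe rule states, not patients. The documents do not say how many patients would reach them; the number is probably small, and only those on ruxolitinib would have a real change in exposure. Section 4.6 draws its thrombocytopenia evidence from myelofibrosis studies with longer and generally higher dosing and reports weaker effects in several other populations. Section 4.3 calls the present dose the lowest efficacious one.

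A reader might infer a bias in the primary comparison. Nothing in the documents supports that, and no effect on the primary estimate is claimed. Minor, but wrong as written.

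**What to change.** In Section 6.5.1, replace both bounded ranges with open-ended ones: when CrCl is below 60 mL/min or there is hepatic impairment of any grade, and platelets are at or below 100 × 10⁹/L, give no more than one tablet per day, with holds below 20 × 10⁹/L governed by Section 6.6.2. The existing return condition can stay.

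This is one wording change, by amendment or investigator letter. It needs no new assessments: haematology and chemistry, including creatinine, are already scheduled in Table 8-1 every other day in hospital and on Days 15 and 29. The cost is that a few more impaired patients, in both arms because the trial is blinded, take one tablet a day.
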